Progestin Primed Double Stimulation Protocol Versus Flexible GnRH Antagonist Protocol in Poor Responders

ClinicalTrials.gov ID: NCT04537078
Date:01/26/2022

AIM OF THE WORK

The primary aim of this work is to assess the difference between the progestin primed double stimulation protocol and the conventional GnRH antagonist protocol in poor responders regarding the number of M2 oocytes retrieved, the fertilization rate, the resultant embryos number, the implantation rate and the clinical pregnancy rate.

While the secondary aims are:

1. Assessing the difference in the ongoing pregnancy rate in both protocols.
2. Assessing the difference between the follicular phase and the luteal phase of the progestin primed double stimulation protocol regarding the total days of controlled ovarian hyperstimulation, the total gonadotropin dosage, the number of M2 oocytes retrieved ,the fertilization rate and the resultant embryos number.
3. Assessing the difference between the follicular phase of the progestin primed double stimulation protocol and the first round of the conventional GnRH antagonist protocol regarding the number of M2 oocytes retrieved the fertilization rate and the resultant embryos number.

PATIENTS

This study is a randomized controlled study performed at infertility and assisted reproduction unit of El-Shatby Maternity Hospital and Madinah Fertility center.

Sample size:

Sample size calculation is done by the staff members of Medical Research Institute, Alexandria University using NCSS PASS statistical software version 20.

Participants:

The study will be conducted on 80 infertile women indicated for ICSI with criteria of poor ovarian response defined by Bologna criteria (15)

All participants will be informed about the nature of the study and informed consent will be taken from all of them.

Inclusion criteria:

1. Indicated infertile women for ICSI of poor responders defined by Bologna criteria either two or more of the following:(15)

- (i) advanced maternal age or any other risk factor for POR.
- (ii) a previous POR ; less than 3-5 oocytes retrieved per cycle.
- (iii) an abnormal ovarian reserve test (ORT): AFC less than 5-7 or AMH is less than 1.1 ng/ml.

Or two episodes of POR after maximal stimulation are sufficient to define a patient as poor responder in the absence of advanced maternal age or abnormal ORT.

Exclusion criteria:

- 1. Male factor infertility due to azoospermia.
- 2. Patients with uncorrected uterine pathology.
- 3. Patients with the diagnosis of severe endometriosis.
- 4. Patients with BMI over 35.

METHODS

Study design:

- Randomized controlled study in which 90 patients will be divided into two groups:

Group 1: 45 patients will be given the progestin primed double stimulation protocol.
Group 2: 45 patients will be given the flexible GnRh antagonist follicular controlled ovarian stimulations will be done in 2 cycles.

- Written informed consents will be obtained from all participants who accept to participate in the research protocol.

Work up:

1. Complete history taking and full assessment of different infertility factors.
2. Hormonal investigations
 - FSH, LH, E2, Prolactin
 - AMH, TSH
3. Basal transvaginal ultrasound

Clinical and embryological procedures:

Group 1:

I. The follicular phase of the double stimulation protocol

- a. luteal phase priming using combined contraceptive pills from day 21 of the previous cycle for one week (0.03 mg ethinyl estradiol, gestodene 0.075 mg, Gynera tab, Bayer Pharma AG., Berlin, Germany).
- b. Controlled ovarian hyper-stimulation with 225-375 IU of gonadotropins will be started day 2-3 of menses after vaginal ultrasound confirming the absence of ovarian cysts.
- c. Dydrogesterone (Duphaston, Abbott company, Illinois, United states) at 20 mg/day will be started from the first day of the ovulation induction.
- d. Patient response will be monitored by:
 1. Transvaginal follicular scanning and the dose of the gonadotropins will be modified according to the response.
 2. Serum estradiol.
 3. Serum progesterone and LH on the day of triggering.
- e. GnRh agonist triggering (Decapeptyl, Ferring, SAINT-PREX Switzerland) in a dose of 2 ampules of 0.2 mg will be administered when leading follicle >18 mm in diameter.
- f. Oocyte pickup will be done 36 hours after GnRh administration with precaution of leaving the follicles measuring 11 mm or less.
- g. After the pick-up, oocytes will be denuded. The denuded oocytes are then assessed for nuclear status. Mature oocytes will be used for ICSI.

II. The luteal phase of the double stimulation protocol

Controlled ovarian hyper-stimulation with 225-375 IU of gonadotropins will be started the next day after the previous oocyte pickup simultaneously with Dydrogesterone (Duphaston, Abbott company, Illinois, United states) at 20 mg/day. The rest will be as the follicular phase.

III. Fertilization and embryo quality:

The fertilization check, which will be performed 16 to 20 hours after ICSI. The resultant embryos will be scored, and they will be vitrified for subsequent transfer.

IV. Embryo transfer

- Starting from the next menstrual cycle Day 3, patients will receive oral estradiol valerate (Cyclo-Progynova (white tablets); Bayer, Germany) daily. From Day 10 onwards, endometrium growth will be monitored by transvaginal ultrasound. When endometrial thickness \geq 7 mm. Progesterone administration (as 800 mg/day vaginal suppositories per day and 100 mg ampule IM every other day) will be initiated and Embryo transfer will be scheduled on Day 3, 4 or 5 with maximum number of 3 class A embryos whether of cleavage or blastocyst stage.

V. Luteal support

- Progesterone administration (as 800 mg/day vaginal suppositories per day and 100 mg ampule IM every other day) will be continued until pregnancy testing 18 days after embryo transfer. The pregnant cases will continue the luteal support till the 12 weeks of gestation.

Group 2:**VI. The flexible GnRH antagonist protocol controlled ovarian stimulation**

This controlled ovarian stimulation will be done twice in two different cycles

In each cycle:

a) luteal phase priming using combined contraceptive pills from day 21 of the previous cycle for one week (0.03 mg ethinyl estradiol, gestodene 0.075 mg, Gynera tab, Bayer Pharma AG., Berlin, Germany).

b) Controlled ovarian hyper-stimulation using antagonist protocol will be used. Stimulation with 225-375 IU of gonadotropins will be started day 2-3 of menses after vaginal ultrasound confirming the absence of ovarian cysts.

c) GnRH antagonist (Cetrotide , Merck Serono, Darmstadt, Germany) will be given daily as the biggest oocyte reaches size 14 mm.

d) Patient response will be monitored by:

1. Transvaginal follicular scanning and the dose of the gonadotropins will be modified according to the response.

2. Serum estradiol.

3. Serum progesterone on the day of triggering.

e) GnRh agonist triggering (Decapeptyl, Ferring, Saint-Prex Switzerland) in a dose of 2 ampules 0.2 mg will be administered when leading follicle >18 mm in diameter. While in the second cycle HCG triggering (Choriomon, IBSA, Lugano, Switzerland) in a dose of 10,000 IU will be administered when the leading follicle >18 mm in diameter.

f) Oocyte pickup will be done 36 hours after GnRh administration.

g) After the pick-up, oocytes will be denuded. The denuded oocytes are then assessed for nuclear status. Mature oocytes will be used for ICSI.

VII. Fertilization and embryo quality:

The fertilization check, which will be performed 16 to 20 hours after ICSI. The resultant embryos will be scored.

Embryos of the first cycle will be vitrified while embryos of the second cycle will be freshly transferred unless there is excess for vitrification for subsequent trials of transfer.

VIII. Embryo transfer

- Progesterone administration (as 800 mg/day vaginal suppositories per day and 100 mg ampule IM every other day) will be initiated on the day of the oocyte pick up of the second cycle. Embryo transfer will be scheduled on Day 3, 4 or 5 with maximum number of 3 class A embryos whether of cleavage or blastocyst stage that will be a mixture of the thawed embryos of the first cycle and fresh embryos of the second cycle.

IX. Luteal support

Progesterone administration (as 800 mg/day vaginal suppositories per day and 100 mg ampule IM every other day) will be continued until pregnancy testing 18 days after embryo transfer. The pregnant cases will continue the luteal support till the 12 weeks of gestation.

Statistical analysis

Statistical analysis of the data

Data were fed to the computer and analyzed using IBM SPSS software package version 20.0. (Armonk, NY: IBM Corp) Qualitative data were described using number and percent. The Kolmogorov-Smirnov test was used to verify the normality of distribution Quantitative data were described using range (minimum and maximum), mean, standard deviation, median and interquartile range (IQR). Significance of the obtained results was judged at the 5% level.

The used tests were

1 - Chi-square test

For categorical variables, to compare between different groups

2 - Fisher's Exact or Monte Carlo correction

Correction for chi-square when more than 20% of the cells have expected count less than 5

3 - Student t-test

For normally distributed quantitative variables, to compare between two studied groups

4 - Mann Whitney test

For abnormally distributed quantitative variables, to compare between two studied groups

5 -Wilcoxon signed ranks test

For abnormally distributed quantitative variables, to compare between two periods

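### Five endpoints share the primary aim, each tested at 5% with no ranking, success rule or adjustment; if any one may count, the type I error is about 10–23%

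*Combined protocol and SAP*

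**What the plan says.** Under AIM OF THE WORK, a single primary aim covers five between-group comparisons: "regarding the number of M2 oocytes retrieved, the fertilization rate, the resultant embryos number, the implantation rate and the clinical pregnancy rate". The secondary aims follow in a separate numbered list, so all five have primary status by the plan's own layout. None is placed above the others.

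The Statistical analysis section gives one rule for all comparisons: "Significance of the obtained results was judged at the 5% level". It then lists tests by type of variable. The only item called a correction is "Correction for chi-square when more than 20% of the cells have expected count less than 5". That item chooses a test for sparse tables and has nothing to do with multiplicity.

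The Sample size paragraph states who did the calculation and with which software. It names no endpoint, effect or power, so it cannot show which of the five the trial was built around.

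**The concern.** A reader cannot tell from the plan what result would count as success. It could be any one of the five, all five, or one that the sponsor has in mind but has not named. Under the first reading, five chances at 5% each do not give a 5% error rate for the primary question.

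The endpoints also differ in kind, running from a laboratory count to clinical pregnancy. More mature oocytes without more pregnancies would support a very different conclusion from the reverse. With no named primary, either could be presented as the main finding once the data are known.

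**Working it through.** **Inputs from the documents**
- Number of primary endpoints: 5 (AIM OF THE WORK).
- Level per test: 0.05 (Statistical analysis).
- Arm size: the Participants section says "The study will be conducted on 80 infertile women indicated for ICSI" (40 per arm if split equally), while Study design says "Randomized controlled study in which 90 patients will be divided into two groups", 45 in each. Both sizes are carried through.

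**Assumptions, because the documents are silent**
- Tests are two-sided, since the aim is worded as a difference.
- Each test has exactly 5% size.
- The correlation among the five test statistics is varied.

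The plan states no family-wise error rate, so there is no figure to reproduce beyond the 5% for a single test.

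**Type I error if any one significant endpoint counts**

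Independent tests: 1 − 0.95^5 = 1 − 0.7738 = 0.2262, or 22.6%.

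Upper bound for any dependence, if each test is valid at 5%: 5 × 0.05 = 25%.

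For equicorrelated normal statistics with common correlation ρ and z = 1.96, the error is 1 − ∫ [Φ((z − √ρ·g)/√(1−ρ)) − Φ((−z − √ρ·g)/√(1−ρ))]^5 φ(g) dg:

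| ρ | Family-wise error |
|---|---|
| 0 | 22.6% |
| 0.3 | 20.9% |
| 0.5 | 18.3% |
| 0.7 | 14.8% |
| 0.9 | 10.2% |

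Only a common correlation above about 0.9 brings the figure below 10%. Independence is the least realistic case, because mature oocytes feed fertilization and then embryo number.

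**Cross-check with linked data.** Data were simulated with no difference between arms. The assumed parameters were a mean of 4 mature oocytes, mean fertilization of 70%, 85% of fertilized oocytes becoming embryos, at most 3 transferred, and mean implantation of 10% or 20%. There were 4,000 replicates per setting. The tests were Mann-Whitney for the first four endpoints and chi-square or Fisher for pregnancy. At least one of the five was significant in 16.4% and 16.5% of trials at 40 per arm, and in 17.5% and 17.2% at 45 per arm.

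**Cost of adjusting.** Holm's first step uses 0.05/5 = 0.01. For a continuous endpoint (two-sample t-test, 80% power):

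| Per arm | Detectable at 0.05 | Detectable at 0.01 | Power at 0.01 for the effect in column 2 |
|---|---|---|---|
| 45 | 0.60 SD | 0.73 SD | 58% |
| 40 | 0.63 SD | 0.78 SD | 58% |

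For clinical pregnancy (pooled-variance normal approximation, 80% power, assumed rate in one arm), the detectable rate in the other arm is:

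| Per arm | Assumed rate | At 0.05 | At 0.01 |
|---|---|---|---|
| 45 | 10% | 34% | 41% |
| 45 | 15% | 41% | 48% |
| 45 | 20% | 48% | 54% |
| 40 | 10% | 36% | 43% |
| 40 | 15% | 43% | 50% |
| 40 | 20% | 49% | 56% |

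**The case against.** The strongest reply is that the inflation depends on a rule the plan never states. Nothing says that one significant endpoint makes the trial positive. If all five were required, the error would be at most 5% without adjustment. This is correct, and it is why the 10–23% is given as conditional. It does not remove the defect: the plan does not require all five either, and as written it lets any one be reported as a positive primary result. Nor does describing the trial as merely assessing differences help, since the plan itself calls these five primary and judges each at 5%.

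Three further points have some force.
- The range is wide and no correlation is documented. The linked simulation, at about 16–18%, is a reasonable middle value, but it also rests on assumed parameters.
- The tests need not have exactly 5% size. For pregnancy, an exact calculation of chi-square with Fisher for sparse tables gives 2.6–3.4% at an assumed 10% rate, 4.6–5.1% at 15% and 5.0–5.4% at 20%. In the other direction, testing fertilization or implantation per oocyte or per embryo would ignore clustering within women and could push the size above 5%; the plan does not state the unit. The 25% bound holds only if each test is valid at 5%.
- The 58% power under Holm is close to a floor, because Holm relaxes the level after each rejection. In simulation with correlations of 0.3 to 0.7, where each affected endpoint had 80% power at 5%, power per endpoint was about 59% with one true effect, 62–63% with three and 68–70% with five.

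These points refine the figures. None supplies the missing success rule.

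**Conclusion.** The concern holds and must be fixed. The plan has five co-equal primary endpoints, a blanket 5% level, and no ranking, success rule, sizing endpoint or multiplicity adjustment. Under the any-one-counts reading, the primary type I error is 22.6% with independence and 10.2% at a common correlation of 0.9. That result assumes two-sided tests of exactly 5% size and an assumed correlation. The absence of a success rule is plain from the text and needs no assumption. The secondary comparisons are outside this calculation.

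**What to change.** Before outcome data are examined, name one of the five as the single primary endpoint, tested at 5%, and move the other four to secondary. One workable choice is the total of mature oocytes per randomised woman over both planned retrievals, with a cancelled or uncompleted retrieval counted as zero so that every woman has a value. Both arms plan two retrievals: Group 1 has a follicular and a luteal stimulation, and for Group 2 the protocol says "This controlled ovarian stimulation will be done twice in two different cycles". The choice of endpoint remains the sponsor's.

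If all five stay primary, or if results by group have already been seen, apply Holm across all five: compare the ordered p-values with 0.05/5, 0.05/4, 0.05/3, 0.05/2 and 0.05, stopping at the first failure. The sponsor should state which situation applies, because the statistical section is written in the past tense and leaves this unclear. A fixed testing order, or a rule that all five must be significant, would also control the error, provided it is set before results are seen.

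**Cost.** With a single primary, four endpoints lose primary status and the named one loses no power. Under Holm, the cost at the first step is the rise in detectable effect tabulated above, for example from 0.60 to 0.73 SD at 45 per arm. The totals of 80 and 90 women must be reconciled before either set of figures is used.

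### The planned trial size is 80 women under Participants but 90 (45 + 45) under Study design, and nothing in the document reconciles the two

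*Combined protocol and SAP*

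**What the plan says.** The PATIENTS section, under Participants, gives the size as a single total: "The study will be conducted on 80 infertile women indicated for ICSI".

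The METHODS section, under Study design, gives a different total, "Randomized controlled study in which 90 patients will be divided into two groups", and then a size for each group. For the double stimulation arm it reads "Group 1: 45 patients will be given the progestin primed double stimulation protocol". The line for the antagonist arm repeats the same number, 45.

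The Sample size paragraph, where one would look to settle the matter, reads in full: "Sample size calculation is done by the staff members of Medical Research Institute, Alexandria University using NCSS PASS statistical software version 20". It contains no number of patients, endpoint, effect size, standard deviation or event rate, power, or attrition allowance. The Statistical analysis section adds only the significance level ("Significance of the obtained results was judged at the 5% level") and a list of tests. It defines no evaluable population.

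**The concern.** Both statements are in the future tense and both describe the women to be studied, yet they differ by 10. The 90 is repeated through the two group sizes, so it is not an isolated slip or a fault in reading the PDF. The document has no amendment log under which either figure could be treated as superseded.

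Planned size is a basic design quantity, and here it has two values. Stopping at 80 departs from the group sizes under Study design; enrolling 90 departs from the Participants section. A reader who later sees the final count would have no fixed figure to judge it against. Because the sizing inputs are absent, nothing else in the document can settle which total the calculation produced.

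**Working it through.** **Inputs from the document.** Total of 80 (Participants); total of 90 and group sizes of 45 and 45 (Study design); 5% significance level, sidedness not stated (Statistical analysis). No other sizing input is given, so neither total can be reproduced from a power calculation.

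**Step 1: internal sums.** 45 + 45 = 90, so the Study design section agrees with itself. Against the Participants section: 90 − 80 = 10 women, or 5 per arm if 80 is split equally. 10/80 = 12.5% and 10/90 = 11.1%. This is too large to be rounding.

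**Step 2: could 90 be 80 inflated for attrition?** With attrition *d*, the usual inflation is n/(1 − d), rounded up.

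| Assumed attrition | Applied to total of 80 | Applied to 40 per arm, doubled |
|---|---|---|
| 5% | 85 | 86 |
| 10% | 89 | 90 |
| 11% | 90 | 90 |
| 15% | 95 | 96 |
| 20% | 100 | 100 |

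For example, 40/0.90 = 44.4, which rounds up to 45 per arm. Working per arm, 45 results only if *d* lies between 1 − 40/44 = 9.1% and 1 − 40/45 = 11.1%. The link is therefore arithmetically possible, but it needs a rate of about 10 to 11% that the document does not state.

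**Step 3: what the difference is worth.** Everything here is an illustration under my assumptions: equal arms, a two-sided 5% level, and a two-sample t-test with results in standard deviation (SD) units.

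- 95% confidence interval half-width = t(0.975, 2n − 2) × √(2/n). At n = 40: 1.991 × 0.2236 = 0.445 SD. At n = 45: 1.987 × 0.2108 = 0.419 SD. The ratio is 1.063, close to √(90/80) = 1.061.
- Detectable difference (noncentral t). At 80% power: 0.634 SD with 40 per arm, 0.597 SD with 45. At 90% power: 0.734 and 0.691 SD.
- Power at 40 per arm if 45 had been the required size: 75.1% where 80% was intended, 86.3% where 90% was intended.
- Clinical pregnancy (two proportions, normal approximation, 80% power, assumed comparator rates):

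| Comparator rate | Detectable rise, 40 per arm | Detectable rise, 45 per arm |
|---|---|---|
| 10% | 26.0 points | 24.2 points |
| 20% | 29.4 points | 27.6 points |
| 30% | 30.7 points | 29.0 points |

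These results all express the same ratio of about 1.06. They are not separate problems.

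**The case against.** The best defence is that the two figures describe different populations: 80 women to be analysed and 90 to be randomised, with roughly 10% allowed for loss. Step 2 shows that the arithmetic permits this. It remains conjecture, because the document states no allowance and labels neither figure. Even if it is true, the text still needs the labels and the rate.

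A second argument is that 90 is the better-supported figure, since it appears as a total and again through both group sizes in the section that sets out the design. That is fair as a reading of the text. It does not show which number the calculation produced, and it leaves the Participants section wrong as written.

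A third argument is that little hangs on the difference. No endpoint, test, allocation ratio or procedure changes, and the loss of precision is small. This largely stands. It is also true that only some outcomes are ambiguous: below 80 both targets are missed, and at 90 or more neither falls short. The uncertainty about a shortfall is confined to final counts of 80 to 89. That narrows the consequence but does not remove the contradiction.

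**Conclusion.** The concern holds. The document gives two incompatible totals for the planned trial size and nothing that reconciles them. The discrepancy of 10 women is certain and rests on no assumption. Its statistical weight is modest: about 6% in interval width, and about 5 percentage points of power if 45 per arm was sized for 80% (80 − 75.1 = 4.9). The power figures depend on the assumed test, sidedness and target power.

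The point must be corrected because planned size is a figure on which the trial relies, not because the loss of precision is large. The document does not show which total is right, and I do not say which is. That the planned power cannot be recovered is a separate gap: it comes from the missing sizing inputs and would remain if the two totals agreed.

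**What to change.** From the output of the sample-size calculation, state one total with matching group sizes under both Participants and Study design.

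- If 80 is the evaluable number and 90 the randomised number, label each as such in both places and give the attrition allowance actually used.
- If the calculation supports only one figure, correct the other to match.

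It would also help to state beside the retained total the endpoint and power it was meant to deliver, although the correction does not depend on this.

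The cost is a wording amendment in two places, with no change to treatment or analysis. The size or power then reported may be slightly less favourable. The document does not say how many women were recruited. If the calculation required 90 and recruitment had followed the 80, the shortfall of 10 would have to be made up or reported.

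### Implantation and clinical pregnancy are primary outcomes, but transfer route is fixed by arm and no pregnancy denominator is stated: they compare whole strategies, not stimulation protocols

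*Combined protocol and SAP*

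**What the plan says.** **Outcomes.** Under AIM OF THE WORK, the primary aim sets the progestin primed double stimulation protocol against the conventional GnRH antagonist protocol on "the number of M2 oocytes retrieved, the fertilization rate, the resultant embryos number, the implantation rate and the clinical pregnancy rate". Ongoing pregnancy is a secondary aim.

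**Group 1 transfer (sections III and IV).** "The resultant embryos will be scored, and they will be vitrified for subsequent transfer". The endometrium is prepared in a separate cycle: "Starting from the next menstrual cycle Day 3, patients will receive oral estradiol valerate".

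**Group 2 transfer (sections VI to VIII).** "This controlled ovarian stimulation will be done twice in two different cycles". Section VII then says "Embryos of the first cycle will be vitrified while embryos of the second cycle will be freshly transferred", with the exception "unless there is excess for vitrification for subsequent trials of transfer". Section VIII starts progesterone on the day of the second pick-up and describes the embryos transferred as a group "that will be a mixture of the thawed embryos of the first cycle and fresh embryos of the second cycle".

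**Analysis.** The Statistical analysis section lists unadjusted two-group tests (chi-square, Fisher or Monte Carlo, t-test, Mann-Whitney), a paired test and a 5% level. Neither it nor any other section defines clinical pregnancy or implantation, gives a denominator, says how women with nothing to transfer are counted, or says whether later transfers contribute.

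**The concern.** The aim names a contrast between stimulation protocols, yet three of its outcomes are observed only after a step that also differs by arm. If pregnancy rates differ, the cause could be the stimulation, the freezing of all embryos, the prepared versus stimulated endometrium, or a combination. A report that follows the aim as worded would credit the stimulation protocol with something the design cannot isolate.

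The missing denominator adds a second difficulty. These are poor responders, and some may have no embryo to transfer. A rate per transfer drops those women after randomisation, and the share dropped may itself depend on the arm. The plan leaves open a per-transfer or a per-woman analysis, and the two can give different answers from the same data.

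**Working it through.** The plan has no figure of its own to reproduce here: it states no pregnancy rate, effect size or power. The first check sets the sections side by side. The second shows, under assumed rates, how far the denominator matters.

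**1. Can stimulation and transfer route be separated?**

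| Feature | Group 1 | Group 2 |
|---|---|---|
| Embryos transferred | all previously vitrified (III) | thawed first-cycle plus fresh second-cycle (VII, VIII) |
| Endometrial setting | later cycle, estradiol-prepared (IV) | second stimulated cycle, progesterone from pick-up day (VIII) |

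Let A be 1 for Group 1 and 0 for Group 2, and let R be 1 for the Group 1 transfer route and 0 for the Group 2 route. Under the plan, R = A for every woman who has the planned transfer. In a model a + b·A + c·R, with b for stimulation and c for route, substituting R = A gives a + (b + c)·A. Only b + c can be estimated, and adjustment cannot divide it. M2 count, fertilization and embryo number are recorded before transfer, so c does not enter them.

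**2. Does the denominator matter?**

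Inputs: 45 women per arm (Study design); two-sided 5% (the plan gives 5% but no sidedness); chi-square, or Fisher when an expected count is below 5. The proportions reaching transfer and the pregnancy rates are assumptions.

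Per-woman rate = proportion reaching transfer × per-transfer rate.

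- Equal per-transfer rates of 20%, reach 70% and 90%: 0.70 × 0.20 = 14% and 0.90 × 0.20 = 18% per woman. No difference per transfer becomes 4 points per woman.
- Equal per-woman counts of 9 out of 45 (20%), reach 90% and 70%: 9/(45 × 0.90) = 22.2% and 9/(45 × 0.70) = 28.6% per transfer. No difference per woman becomes about 6.3 points per transfer.

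Simulated share of trials in which the two tests fall on opposite sides of p = 0.05, with equal 20% per-transfer rates:

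| Reach, the two arms | Tests disagree |
|---|---|
| 80% / 80% | about 2% |
| 75% / 85% | 3% to 4% |
| 70% / 90% | about 7% |

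Simulated power with per-transfer rates of 20% and 35%:

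| Reach (20% arm / 35% arm) | Per-woman rates | Power per transfer | Power per woman |
|---|---|---|---|
| 90% / 70% | 18.0% / 24.5% | about 30% | about 12% |
| 70% / 90% | 14.0% / 31.5% | 28% to 29% | 52% to 53% |

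A per-woman analysis can therefore lose or gain power. It answers a different question, so the choice should be made in advance and not by result.

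**3. Implantation.** Each transfer may use up to 3 embryos (IV, VIII). A chi-square test on embryos treats those from one woman as independent, although they share a uterus and a cycle.

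**The case against.** The best defence is that a protocol here means everything done in an arm. The Study design section uses the protocol name as the label for Group 1, and transfer is described within each group's run of sections. Part of the route also follows from the regimen: Group 1 starts its second stimulation the day after the first pick-up. On that reading the trial compares two strategies, which randomisation supports. This largely stands, and it is why the remedy is a matter of wording. It does not settle the matter, because the aim never says so and the protocol headings (I, II, VI) cover stimulation while transfer has its own (IV, VIII).

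It can also be said that each arm schedules one transfer and one pregnancy test 18 days later, so that transfer is the natural one to count. That is reasonable, but the text does not say it, and it leaves the denominator open.

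A reader might infer more than the documents support:

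- *The randomised comparison is invalid.* It is valid for complete strategies.
- *Transfer route inflates the false-positive rate.* From a 20% base with 45 per arm, an assumed route effect of 5, 10 or 15 points upward gives p<0.05 in about 9%, 20% or 37% of trials. That is ordinary power to detect a real strategy difference.
- *Group 2 gets extra chances of pregnancy.* Later transfers are mentioned only for Group 2, but Group 1 may also hold surplus frozen embryos, and silence does not exclude their use. No section establishes later transfers in one arm only.
- *Second-round timing and pill priming are further confounders.* They are part of what defines the two regimens.
- *Only the comparison of "the follicular phase of the progestin primed double stimulation protocol and the first round of the conventional GnRH antagonist protocol" (secondary aim 3) can say anything about stimulation.* Oocyte, fertilization and embryo outcomes are free of transfer route, so so broad a restriction is not needed.

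**Conclusion.** The concern holds in a limited form. Transfer route and endometrial setting coincide with arm, so implantation, clinical pregnancy and ongoing pregnancy can be read only as outcomes of whole strategies. This follows from the text and needs no assumed rate. The other three primary outcomes are untouched by it, and all five can stay primary.

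The missing denominator would be only a missing detail by itself, but it leaves open an analysis that excludes randomised women. Its size depends on how many women reach transfer in each arm, which the documents do not give. It is small if the arms are alike (about 2% disagreement at 80% each) and larger if they are not (about 7% at 70% and 90%). These figures illustrate the assumed rates and do not predict this trial's result. They use 45 per arm; the Participants section gives a total of 80 instead of 90, which is a separate matter.

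**What to change.** 1. State in the aims that implantation, clinical pregnancy and ongoing pregnancy compare complete strategies, meaning stimulation together with transfer route, and that a difference in them will not be credited to stimulation alone.
2. Analyse clinical and ongoing pregnancy per woman randomised, counting women without a transfer as not pregnant. Report the number without a transfer in each arm.
3. State whether the primary count uses the first planned transfer or all transfers. Apply the same rule and time window in both arms, and report the other count as supportive. Either is defensible: the first is simpler, the second closer to a full strategy.
4. Label implantation per embryo as describing only women who reached transfer, and use an analysis that allows for several embryos from one woman.
5. The Statistical analysis section is written in the past tense. If outcomes have already been seen, date these changes and label them as set afterwards.

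The cost is a few sentences, a narrower claim and per-woman rates that look lower than per-transfer rates. Power may move in either direction. None of this proposes a trigger, pick-up or transfer rule.
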